Study protocol:

Sex-unique disparities in survival and resuscitation after out-of-hospital cardiac arrest – a Danish analysis

Study type

Observational study

Unique protocol identification number

ohcagd2022

Background

With the recent emphasis on research in womens' health, sex differences in OHCA are nowadays more often investigated worldwide and mounting evidence revealed sex as a possible modifier of outcome in cardiovascular disease (CVD)^{1 2 3 4 5}. Cardiovascular disease (CVD) is the leading cause of death in women, although conventionally, it has been considered as a male dominated disease⁶. In contrast to common beliefs, heart attacks occur almost as frequently in women as in men, but at an older age and with clinical manifestations that vary between, younger, premenopausal and older postmenopausal women^{7 8 9}.

Previous studies have investigated sex differences in OHCA, but with limited comprehensiveness and conflicting results regarding reported survival between sexes^{10 11 12 13 14}. These discrepancies may be explained by the fact that data is assessed in different countries with different health care systems, with divergent inclusion criteria and subgroups of age, e.g. selection for only shockable initial rhythm (SIR)¹⁴. This suggests further investigations and cohesion to a standardized and comprehensive view on sex differences in OHCA outcomes.

In 2016 the Danish Emergency Medical Services introduced a nationwide electronic reporting system. This registry allows electronic searches to evaluate subgroups of OHCA (out-of-hospital cardiac arrest). Hence, it became possible to investigate characteristics in OHCA related to sex differences. Therefore, with this population-based cohort-study, we plan to analyze all emergency medical services treated resuscitations in Denmark between 2016 and 2021. This serves to achieve a better understanding and enhanced knowledge of the epidemiology of OHCA in between different sexes.

Aim

In this study we aim to describe possible differences in help provision by bystanders, cardiopulmonary resuscitation (CPR), pre-hospital treatment by emergency medical services (EMS), presence of SIR and survival rates after OHCA at successive stages of treatment for a six-year period in a Danish setting.

Methods

This study is a registry-based follow-up, including data on OHCA collected in the electronical prehospital medical registrations recorded by the Danish Emergency Medical Service over a 6-year period from 2016 to 2021.

Data

This analysis will be based on data from the national electronic based Danish OHCA registry. Data on OHCA with resuscitative attempts in Denmark have been collected in the electronic based Danish Medical Service report system since 2016. The registry covers detailed data including the EMS report, executive entries, and advanced text searches of prehospital charts. All cases go through an elaborate validation process where all identified events are read through manually by an external verification team. This ensures high quality of data, collected according to the Utstein recommendations, throughout the approximately 5400 cases of OHCA in Denmark annually. During this verification process, supplementary sources of data are linked to each OHCA, among others information about survival, localization, initiation of bystander CPR and EMS personnel operation.

Variables included

- **Age:** Age will be defined as the patient's age at the time of the event. Subjects will be stratified into six age-groups, including <40 years of age, 40-49 years of age, 50-59 years of age, 60-69 years of age, 70-79 years of age, over 80 years of age.
- **Sex:** Sex will be stated as either male, female or undetermined and derived from personal identification numbers. Gender will be defined based on EMS-charts, in cases where an

identification number is not found.

- **Initial rhythm:** The initial rhythm recorded by manual defibrillator or AED (whichever first) will be defined as the first rhythm observed by EMS personnel and categorized as either shockable initial rhythm ((SIR), ventricular tachycardia, ventricular fibrillation), non-shockable (asystole, pulseless electrical activity), non-shockable (other) or undetermined.
- **Etiology of cardiac arrest:** Presumed causes will be stated as either presumed cardiac, other medical cause, trauma, drug overdose, drowning, electrocution, or hypoxemia (external).
- **Location of Incidence:** Location will be characterized as either: privat home, public space, outdoor nature or other.
- **Observation of occurrence:** OHCAs will be defined as either unwitnessed, bystander witnessed or EMS-witnessed.
- **Cardio-pulmonary-resuscitation (CPR):** CPR will include bystander-initiated CPR and EMS treatment with CPR.
- **Deployment of automatic external defibrillators (AEDs):** Defibrillation will include defibrillation by bystanders and/or EMS personnel. This includes using publicly available AEDs, which are fitted to the patient, have analysed the rhythm, but did not deliver a shock.
- **EMS-response time:** This will be defined as the time between a dispatcher receiving the emergency call and the arrival of the first EMS-personnel.
- **Hospitalization:** Hospitalization will be considered as either: transported to hospital or declared dead by EMS-personnel.
- **Return-of-spontaneous-circulation (ROSC):** ROSC will be classified as the achievement of ROSC anytime between recognition of the event and termination (defined as either hospital admission or declaration of death by EMS-personnel).

- **State at hospital admission:** State of the case upon arrival at the hospital will be defined as either ROSC or ongoing CPR.
- **Survival:** Survival will be defined as ROSC at the time of hospital admission, additionally 30-day survival will be included, this derived from data from the National Patient Registry. Survival will be calculated in total, per age decade and after selection for SIR. Survival will also be stratified according to location of OHCA (at non-public versus public location).

Analysis

Data is collected using the STrengthening the Reporting of OBservational studies in Epidemiology (STROBE) statement. All percentages will exclude missing values. Descriptive statistics includes the above-mentioned variables identified with absolute numbers and percentages. Comparative analyses will be carried out using non-parametric testing to examine subgroups. Forward logistic regression analysis will be performed for multivariate analysis. Odds ratio for survival will be calculated stratified by localization, bystander, SIR and EMS-actions.

Data storage

Data is stored on secure drive according to the regional instructions for safe conduct of data management.

Overall recruitment status
Completed.

Ethical considerations

GDPR will be followed according to Danish law, and the study is registered and approved at the Danish Data Protection Agency, capital region of Denmark. Since it is a registry-based study, no ethical approval is required.

Perspectives

This study will provide updated information regarding OHCA for the association of sex, bystander actions and survival, based on a reviewed, high-quality database. Findings might contribute to enhanced knowledge upon circumstances and potential modifiable factors associated with increased survival. Thus, it is our hope that this study will contribute to improve handling this type of arrests. This, eventually using educational campaigns targeted laypersons and healthcare personnel.

List of Abbreviations

AED: Automatic External Defibrillator

CPR: Cardio Pulmonary Resuscitation

EMS: Emergency Medical Services

GDPR: General Data Protection Regulation

OHCA: Out-of-Hospital Cardiac Arrest

ROSC: Return of Spontaneous Circulation

SIR: Shockable Initial Rhythm

STROBE: STrengthening the Reporting of OBservational studies in Epidemiology

6. Global Burden of Disease Collaborative Network. Global Burden of Disease Study 2019 (GBD 2019).

Seattle, United States of America: Institute for Health Metrics and Evaluation (IHME).

doi:<https://doi.org/10.6069/1D4Y-YQ37>

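### The top age band has no upper limit and the band-wise survival tests make no age adjustment, so part of any sex difference among the oldest patients may be age

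*Protocol*

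**What the plan says.** In the Protocol, under Variables included, Age is defined at the event ("Age will be defined as the patient's age at the time of the event") and then cut into six groups, the last two being "70-79 years of age, over 80 years of age". Under Survival in the same list: "Survival will be calculated in total, per age decade and after selection for SIR". Two outcomes are named there: "Survival will be defined as ROSC at the time of hospital admission, additionally 30-day survival will be included".

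Under Analysis, the comparison method is "Comparative analyses will be carried out using non-parametric testing to examine subgroups". No age adjustment within a subgroup is mentioned. The other two statements there are "Forward logistic regression analysis will be performed for multivariate analysis", which does not say whether or in what form age enters, and "Odds ratio for survival will be calculated stratified by localization, bystander, SIR and EMS-actions", which does not list age among the strata.

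The Background says of heart attacks that they occur in women "but at an older age and with clinical manifestations that vary" with age group.

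**The concern.** The question of the study is sex, and a band-wise test relies on the band alone to make women and men comparable in age. A closed ten-year band does this fairly well, because the sexes cannot differ much in mean age inside it. An open band does it less well: whatever age difference remains in the upper tail stays in the comparison. If survival falls with age and women in the band are older, the test charges that age difference to sex.

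At stake is the reading of the oldest group, roughly a quarter of cases under the assumptions below. A small deficit for women there, beside nearly unbiased bands at younger ages, could be taken for a sex disparity that appears only in old age. The Background invites readers to look for a pattern by age. The top band is also not a decade, so the Age and Survival entries do not match each other.

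**Working it through.** The protocol states no sample size, significance level, effect size or age distribution, so it has no figure to reproduce. What follows is a sensitivity calculation.

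**From the protocol.** About 5,400 cases a year over 6 years: 5,400 × 6 = 32,400.

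**Assumed.**
- 35% of cases are women.
- Mean ages (men/women) are 70/73, 69/74, 68/73 or 70/75, with the same SD (13 to 16) in both sexes.
- Ages are whole years, normal in shape and cut off at 105. The top band is read as 80 and over.
- Log-odds of survival fall by β = 0.03 to 0.07 per year (odds down 3-7%), with no sex effect.
- Survival in the band is 5%, or 20% (for example ROSC at admission).
- Tests are two-sided at 5%. The protocol names neither the test nor the level, so a Wald test stands in.

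**Formulas.** For sex s, the weight of age a within the band is w_s(a) ∝ exp(−(a − μ_s)²/2σ²). Survival at age a is p(a) = 1/(1 + exp(−c + β(a − 80))), with c set to give the chosen overall survival. Then:
- P_s = Σ w_s(a)·p(a)
- OR = [P_f/(1 − P_f)] / [P_m/(1 − P_m)]
- SE = √[1/(n_m·P_m(1 − P_m)) + 1/(n_f·P_f(1 − P_f))]
- z = ln(OR)/SE
- type I error = Φ(−1.96 − z) + Φ(−1.96 + z)

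**Worst case of the grid** (means 70/75, SD 13, β = 0.07, survival 20%).
- The band holds 4,843 men and 4,065 women, and women are 1.05 years older within it.
- P_m = 0.2047 and P_f = 0.1944, so OR = (0.1944/0.8056)/(0.2047/0.7953) = 0.94.
- SE = √[1/(4,843 × 0.1628) + 1/(4,065 × 0.1566)] = 0.053.
- z = −0.0643/0.0533 = −1.21.
- Type I error = Φ(−0.75) + Φ(−3.17) = 0.226 + 0.001 = 23%.

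**Mildest case** (means 70/73, SD 16, β = 0.03, survival 5%). Women are 0.50 years older, OR = 0.986, SE = 0.097, z = −0.15, type I error 5.2%.

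**Whole grid.**

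| Band | Women older by (years) | Age-only OR | Type I error, survival 5% | Type I error, survival 20% |
|---|---|---|---|---|
| 70-79 | 0.1-0.2 | 0.98-1.00 | 5% | 5-6% |
| 80 and over | 0.5-1.05 | 0.94-0.99 | 5-10% | 6-23% |
| 80-89 | 0.1-0.2 | 0.98-1.00 | 5% | 5-6% |
| 90 and over | 0.2-0.5 | 0.97-0.99 | 5% | 5-6% |

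The open band holds about 7,400-9,800 cases. In survival itself, the age-only gap there runs from 0.1 to 0.3 percentage points at 5% survival and from 0.2 to 1.0 at 20%.

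**Sensitivity.**
- Unequal spread: SD 14 in men and 15 in women gives OR 0.92-0.97. SD 16 in men and 13 in women gives 1.01-1.05, so the bias changes sign.
- Age cut-off: 100 instead of 105 gives OR 0.95-0.99, and 110 gives 0.93-0.98.
- A different age model (truncated exponential over 80-105, women taken as 0.5-2 years older within the band) gives 0.89-0.99. The lower end needs both a 2-year gap and a 7% fall in odds per year.

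**The case against.** The strongest reply has four parts.

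- **The SAP.** How age enters a regression is ordinary SAP content, and the SAP is not shown. This stands. A reader might infer that age is used only in six groups throughout, but the protocol does not say so, and the forward logistic regression may well carry age in years. The point is therefore confined to the band-wise comparison. A regression elsewhere in the report does not repair that comparison.
- **The band-wise test is partly inferred.** The protocol says survival is calculated by age group and that subgroups are tested. It states no sex odds ratio by band and no 5% level. This stands as a limit on the type I error figures. A women-versus-men test within age groups is still the natural reading, given the study's question.
- **The age premise is not documented for this population.** A reader might infer from the Background that women in the top band are older than men. The sentence concerns heart attacks in general, not cardiac arrest and not patients over 80. This stands, and it is why the direction is called likely only.
- **The effect is small, and an open top band is a common convention.** This is largely true. The normal model puts about 30-40% of the band at 90 or over. If that group is really smaller, the age gap and the bias shrink.

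None of this disputes that the band is open-ended or that no age adjustment within a band is stated.

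**Conclusion.** The point holds as an optional, low-cost improvement. The open top band does not match the promise of survival by decade, and it controls age less well than the closed bands in a comparison that has no other stated age control.

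Under equal SDs and women 3-5 years older on average, the age-only OR is about 0.94-0.99, with a type I error of 5-10% at 5% survival and 6-23% at 20%. It is a modest distortion, more relevant to ROSC at admission than to an outcome near 5%.

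Two stronger readings are not supported. One is that the study will show a deficit for women that is only age: the direction depends on how dispersed women's and men's ages are, which the protocol does not give. The other is a larger bias: a type I error of about 35% at 20% survival, for example, arises with means 69/74 and β = 0.07 only once women's SD is raised to 15 against 14 in men.

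**What to change.** Keep the age bands for description. Add one sentence under Analysis: the women-versus-men difference in survival within each age band, at the least the top one, is estimated from a logistic model with sex and age in years (linear, or a spline if the fit requires it). If the form of age is right, the age-only OR becomes 1.00 by construction. Under Age, replace the open band by 80-89 and 90 and over, so that it matches the reporting by decade. Splitting alone already brings the age-only OR to 0.98-1.00 and 0.97-0.99.

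No new data are needed: age at the event is already defined, and cutting bands in years implies that it is held in years. The cost is one extra table row and a less precise estimate at 90 and over. In the same model, the SE of the log OR there is 0.15-0.20 at 5% survival, against 0.09-0.11 in the pooled band. At SE 0.20 the 95% limits lie a factor of exp(1.96 × 0.20) = 1.48 either side of the estimate. The age-adjusted estimate for everyone aged 80 and over can be shown beside the two rows to keep the precision.

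### Does excluding missing values from all percentages remove on-scene deaths from the survival denominators and distort the comparison of women and men?

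*Protocol*

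**What the plan says.** The rule is one sentence in the Analysis section of the protocol: "All percentages will exclude missing values". What counts as missing is not defined.

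These entries under Variables included bear on it:

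- Hospitalization: "Hospitalization will be considered as either: transported to hospital or declared dead by EMS-personnel". On-scene deaths are therefore in the cohort and recorded as deaths.
- State at hospital admission: "State of the case upon arrival at the hospital will be defined as either ROSC or ongoing CPR". There is no category for a patient who never arrived.
- Survival: "Survival will be defined as ROSC at the time of hospital admission, additionally 30-day survival will be included", the latter "this derived from data from the National Patient Registry". The entry adds that survival is computed overall and in subgroups of age, rhythm and location.
- Sex: "Gender will be defined based on EMS-charts, in cases where an" identification number cannot be found.

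The Data section says that during verification "supplementary sources of data are linked to each OHCA, among others information about survival". The Background sets the population as every resuscitation treated by EMS in Denmark from 2016 to 2021. The Aim is to describe survival "at successive stages of treatment for a six-year period".

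**The concern.** The study compares women and men on survival, so the denominator matters. Two routes to a wrong one suggest themselves.

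The first concerns admission. A patient declared dead on scene has an empty field for state at admission. If ROSC at admission were tabulated from that field and empty fields were dropped, the result would be a percentage of transported patients. Should the share dying on scene differ by sex, the comparison could shrink, grow or appear from nothing. ROSC at any time would meanwhile keep the on-scene deaths, because its window closes at admission or at declaration of death. Two neighbouring stages would then rest on different denominators without the reader knowing.

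The second concerns 30-day survival. It comes from a registry, and the protocol foresees patients without an identification number. It gives a substitute source for their sex but none for their survival. If they could not be linked, the rule would drop them, including those whom EMS had declared dead.

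**Working it through.** **Step 1: what the text requires.** The transported-only result follows only if both of these hold:

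| Needed for the feared reading | What the protocol has |
|---|---|
| Survival is computed from state at hospital admission | Survival is a separate entry with its own definition; no derivation from the other variable is stated |
| An on-scene death is a missing value | Hospitalization records it as a death; the state variable describes patients on arrival and so does not apply |

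Neither holds on the page. The stated cohort (all EMS-treated resuscitations), the Aim (survival after OHCA, not after transport) and the instruction to compute survival overall all point to all patients as the denominator. None of them is a formal definition, but none points the other way.

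**Step 2: size at admission if the feared reading were applied.** The plan states no rates, so there is no figure of its own to reproduce. All percentages below are assumptions. Let *p* be the share of all patients with ROSC at admission and *d* the share declared dead on scene. Everyone with ROSC at admission was transported, so

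share among transported = *p* / (1 − *d*), and odds ratio (OR), women versus men = [*p*w/(1 − *p*w)] / [*p*m/(1 − *p*m)].

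| *p* men / women | OR, all patients | *d* men / women | Transported only, men / women | OR, transported only |
|---|---|---|---|---|
| 26% / 22% | 0.80 | 38% / 45% | 0.26/0.62 = 41.9%; 0.22/0.55 = 40.0% | 0.92 |
| 26% / 22% | 0.80 | 40% / 40% | 0.26/0.60 = 43.3%; 0.22/0.60 = 36.7% | 0.76 |
| 26% / 22% | 0.80 | 45% / 38% | 0.26/0.55 = 47.3%; 0.22/0.62 = 35.5% | 0.61 |
| 24% / 24% | 1.00 | 38% / 45% | 0.24/0.62 = 38.7%; 0.24/0.55 = 43.6% | 1.23 |
| 24% / 24% | 1.00 | 40% / 40% | 40.0%; 40.0% | 1.00 |

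A second set of assumptions shows the same pattern. With *p* = 25% in both sexes and *d* = 40% in men, the OR is 1.00, 1.17 or 1.40 for *d* = 40%, 45% or 50% in women. With *p* = 25% in men and 20% in women (OR 0.75 on all patients), it is 0.70, 0.93 or 1.12 for *d* = 40%, 50% or 55% in women.

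With equal *d*, the factor 1/(1 − *d*) cancels from the ratio of the two percentages: 0.22/0.26 = 0.85 on either denominator. The OR still moves a little (0.80 to 0.76) because both percentages are higher. The larger shifts all need a sex gap in on-scene death, here 5 to 15 points, which the documents do not give.

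**Step 3: size at 30 days.** Let *u* be the share of patients dropped as unidentified, all assumed dead, with true 30-day survival of 14% in both sexes. The reported percentage is 0.14/(1 − *u*).

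- *u* = 3% in men, 1% in women: 14.43% and 14.14%, a false difference of 0.29 points.
- *u* = 5% in men, 1% in women: 14.74% and 14.14%, a false difference of 0.60 points.
- *u* = 3% in both: no difference.

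If the unidentified survive as often as the rest, nothing changes whatever the shares. Whether any such loss occurs is itself an inference: the Data section speaks of survival information linked to each case, and nothing says that linkage fails where sex was taken from the EMS chart.

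**The case for a change.** The strongest case for a change is that the protocol does more than stay silent. It fixes a rule for every percentage and, beside it, a variable with an empty cell for a whole class of patients. A programmer who tabulates state at admission by sex and drops the blanks would be following the sentence as written. The phrase about successive stages can also be read as survival among those who reach each stage. The Background itself blames conflicting earlier results partly on differing inclusion criteria, so an unstated denominator is awkward here, and stating it would cost a sentence and no new data.

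Part of this stands. The denominator and the meaning of missing are not written down, and such a tabulation is possible. But that table would describe state on arrival, for which transported patients are the proper denominator. It would become wrong only if presented as survival of all arrests, which contradicts the stated cohort. A figure among transported patients is also a legitimate conditional result in a study of successive stages, so the residual risk is one of labelling. Best- and worst-case bounds for unknown 30-day status would be a matter of preference, since no loss is documented.

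**Conclusion.** No change follows. Leaving missing values out of percentages is an ordinary descriptive convention, and a patient recorded as dead on scene is not missing for survival. The natural reading counts such patients as without ROSC at admission and as dead at 30 days, with all included patients of each sex as the denominator. What is left is a minor gap in wording, of the kind an analyst fills sensibly or a statistical analysis plan settles.

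The possible size is not trivial if the gap were filled badly: under assumed rates, an OR of 1.00 could become 1.23 with a 7-point sex gap in on-scene death, or 1.40 with a 10-point gap. These figures depend on both a strained reading and undocumented sex gaps. At equal shares a null difference stays null. The 30-day part is at most 0.60 points under the assumed shares in step 3, and ROSC at any time is unaffected. The conclusion would change only if survival were in fact derived from the state-at-admission field with blanks dropped and then reported as survival of all arrests; the protocol does not call for that.

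### Forward selection is the only multivariable method and sex is not kept in the model, so a null or small adjusted sex odds ratio for survival may go unreported

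*Protocol*

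**What the plan says.** All quotes are from the Protocol.

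- **Analysis**, on multivariable modelling: "Forward logistic regression analysis will be performed for multivariate analysis". This is the only such sentence. It names no outcome, candidate list, entry threshold or forced term.
- **Analysis**, on the other odds ratios: "Odds ratio for survival will be calculated stratified by localization, bystander, SIR and EMS-actions". Age is not among the stratifiers, and the contrast is not named as sex. The remaining comparisons are non-parametric subgroup tests, which are unadjusted.
- **Variables included, Survival**: "Survival will be calculated in total, per age decade and after selection for SIR". Survival is also to be split by public versus non-public location.
- **Background**, on age: "heart attacks occur almost as frequently in women as in men, but at an older age".
- **Aim**: the study will describe "possible differences in help provision by bystanders, cardiopulmonary resuscitation (CPR), pre-hospital treatment by emergency medical services (EMS), presence of SIR", as well as survival rates.
- **Perspectives**: the study is to give "updated information regarding OHCA for the association of sex, bystander actions and survival". The title likewise puts sex disparities in survival first.

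**The concern.** In a study of one named exposure, whether that exposure's estimate is reported should not depend on its own p-value. Ordinary forward selection makes it depend on exactly that. If sex fails the entry test, the final model has no sex coefficient and no interval. If sex enters with a true effect near the threshold, the printed estimate is on average too far from 1, because only the larger estimates get through.

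The other planned outputs do not replace the lost estimate. The Background says women have heart attacks at an older age than men, so a sex comparison that ignores age is open to confounding. Stratifying by location, bystander, rhythm and EMS action does not deal with age. Survival by decade shows age-specific rates but gives no pooled age-adjusted OR with an interval.

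What is at stake is mainly a near-null result. The Background motivates the study by conflicting reports on survival between the sexes. An adjusted OR close to 1 with a narrow interval would bear directly on that conflict, and it is the result this method is most likely to leave out.

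**Working it through.** The Protocol states no sample size calculation, alpha or entry threshold, so there is no figure of its own to reproduce. The calculation below shows how often sex would enter.

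**Inputs**

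- From the Protocol (Methods and Data): about 5,400 cases a year over six years, so N = 5,400 × 6 = 32,400.
- Assumed: survival s = 12% (range 8-25%), share of women q = 35% (range 30-40%), entry at two-sided p<0.05.

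**Standard error of the log OR**

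SE = 1/√[N·s(1−s)·q(1−q)] = 1/√[32,400 × 0.12 × 0.88 × 0.35 × 0.65] = 1/√778.4 = 0.0358.

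This leaves out the correlation of sex with the other covariates, which would raise the SE and lower the entry rates somewhat.

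**Entry probability**

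With m = ln(OR)/SE, P(enter) = Φ(−1.96 − m) + 1 − Φ(1.96 − m). The average reported OR is the exponential of the mean log OR among estimates with |z| > 1.96.

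For OR 0.95: m = −0.0513/0.0358 = −1.43, so P(enter) = Φ(−0.53) + a negligible upper tail ≈ 0.30.

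| True adjusted OR | Enters, base case | Average OR when entered | Enters, over the ranges |
|---|---|---|---|
| 1.00 | 5% | – | 5% |
| 0.95 | 30% | 0.91 | 21-50% |
| 0.92 | 64% | 0.90 | 46-89% |
| 0.90 | 84% | 0.89 | 65-98% |
| 0.85 | 99.5% | 0.85 | 95-100% |

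The low ends come from 8% survival and 30% women (SE 0.0447), the high ends from 25% survival and 40% women (SE 0.0262).

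**Where entry becomes a coin toss**

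exp(−1.96 × 0.0358) = 0.93. A true adjusted OR between about 0.93 and 1 is left out more often than not.

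**Check by simulation**

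Forward selection was run on simulated data with N = 32,400, five candidates (sex, age, rhythm, location, bystander) and 100 runs per scenario. Sex entered in 7%, 26% and 61% of runs for true ORs of 1.00, 0.95 and 0.90. At 0.95 the entered runs averaged 0.90. With sex forced in, the mean ORs were 1.01, 0.94 and 0.91, so forcing removed the inflation. Entry at 0.90 is lower than in the closed form because the SE in the simulation was about 0.044.

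**What would be printed with sex forced in**

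With an SE of 0.040, which allows for the other covariates, an estimate of 0.95 has a 95% CI of about 0.88 to 1.03, and an estimate of 1.00 about 0.92 to 1.08. Both are informative.

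**The case against.** The strongest counter-argument is that the point rests on silence. The sentence is generic, a forward procedure can start from forced terms, and a statistical analysis plan that is not shown may force sex in. This stands in part. That sex is reported only if it passes the test is the default reading of the method, not stated text. But the Protocol is not simply silent, because it names data-driven entry as its multivariable method. A later plan that forced sex in would be correcting that choice.

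Second, the Aim is descriptive, and Perspectives also speaks of modifiable factors linked to survival, a purpose that a forward model could serve. The forward model's outcome is not named either; survival is the natural reading. All this is fair, but the title and Perspectives still make sex and survival a main question, and no other multivariable model is planned for it.

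Third, rates by age decade and the stratified ORs, if made by sex, would be reported whatever the entry test shows. This stands. A reader might infer that the plan could hide a sex difference in survival, and the documents do not support that: crude and age-specific differences would remain visible. What is missing is a guaranteed age-adjusted OR with its interval.

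Fourth, moderate effects survive selection. This also stands, and it bounds the harm.

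A reader might further blame forward selection for any gap between an age-adjusted sex OR and one also adjusted for rhythm, location and bystander help. That gap comes from which covariates are adjusted for, and many of these are things the Aim sets out to compare between the sexes. It would exist with any selection method.

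**Conclusion.** The point holds in limited form and should be fixed. As written, the Protocol gives the study's exposure no protection in its only multivariable model, and no other planned analysis guarantees an age-adjusted sex OR with a confidence interval. The loss and the inflation concern adjusted ORs near 1: at a true 0.95, about 30% entry (21-50%) and an average of about 0.91 when entered. At 0.90 the loss is modest (84% entry, range 65-98%), and at 0.85 it is negligible (95-100%).

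Only the annual case count comes from the Protocol. Survival, share of women and entry threshold are assumptions. The conclusion also rests on reading forward regression in its ordinary sense, and an unseen analysis plan could already resolve it. No claim is made that the set of selected covariates would be unstable at this sample size.

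**What to change.** Replace the sentence on forward regression with:

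> For each survival outcome (ROSC at hospital admission; 30-day survival), logistic models are fitted with sex (male/female; undetermined sex excluded and counted) and the six age groups kept in every model regardless of p-value. Model 1 contains sex and age group only and gives the age-adjusted sex difference. Model 2, labelled explanatory, adds prespecified covariates (location, witnessed status, bystander CPR, bystander defibrillation, EMS-response time, initial rhythm, etiology) without stepwise selection. The sex OR with 95% CI is reported from each model. Hospitalization, ROSC and state at admission are not covariates.

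The AED item under Variables included says "Defibrillation will include defibrillation by bystanders and/or EMS personnel", so the bystander part has to be taken separately for Model 2.

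The cost is one paragraph of wording and no new data. There are two small downsides. Some non-significant covariates stay in Model 2, and part of the difference between the two sex ORs is non-collapsibility of the odds ratio rather than explanation by the added covariates. Excluding EMS-witnessed arrests from Model 2 and pooling rare etiology levels are optional choices and not part of this fix.
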